14.3.2.3 Part B analysis for subjects who experience a flare

For subjects who experience a flare during Part B, the secondary efficacy variables listed below will be analyzed. The timepoint for these secondary efficacy analyses will be at Escape Week 12).

- ASDAS disease activity (ASDAS-ID, ASDAS-MD, ASDAS-HD, and ASDAS-vHD)
- ASDAS clinical improvement (ASDAS-CII, ASDAS-MI)
- ASAS20, ASAS40, ASAS5/6, and ASAS PR response
- Change from Baseline in ASDAS, BASDAI, BASFI, and BASMI
- Change from Baseline in MRI

These variables will be summarized by treatment group using descriptive statistics. For the binary response variables (ASDAS-CII, ASDAS-MI, ASAS20, ASAS40, ASAS5/6, and ASAS PR), counts and percentages at Escape Week 12 visit will be displayed. For comparative purposes, the tables will also include the responder counts and percentages at the visit where flare criteria were met. ASDAS disease activity will be summarized in a similar way based on the 4 categories.

For the continuous variables (ASDAS, BASDAI, BASFI, BASMI), quantitative descriptive statistics by treatment group will be displayed. This summary will include the actual results at Escape Week 12, change from Baseline (Week 0), change from randomization Baseline (Week 48), and change from the visit in which the flare occurred.

All Part B summaries after subjects experience a flare will be based on observed case data and will use the FS.

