3.2 Secondary objectives

The secondary objectives are to:

- Evaluate the percentage of subjects achieving sustained remission at the end of Part A
- For subjects randomized into Part B:
 - Evaluate the time to flare and other measures of signs and symptoms
 - Compare the percentage of subjects who do not experience a flare between CZP full-dose and half-dose
 - Evaluate the efficacy of re-initiation of treatment with the CZP full-dose in subjects who experience a flare following a withdrawal or dose reduction of CZP
- Assess safety and tolerability of CZP
- Evaluate inflammatory changes over time as assessed by MRI

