6.3.2 Escape treatment

Subjects receiving placebo or half-dose CZP (200mg Q4W) who experience a flare during the Double-Blind Period will escape to full-dose treatment (CZP 200mg Q2W) until the end of that period or for at least 12 weeks, whichever is longer. The escapers need to come back to the site at the timepoint of the escape (Week 0), 2 and 4 weeks after escape (Weeks 2 and 4), and every 12 weeks thereafter until the originally scheduled Week 96.

Subjects escaping from placebo to full-dose CZP (200mg Q2W) will receive a loading dose of CZP (400mg Q2W; 2 injections) at the 3 consecutive visits after the flare. Subjects escaping

from half-dose CZP to full-dose CZP will receive a loading dose of CZP 200mg Q2W at the 3 consecutive visits after the flare. In order to maintain the blind, subjects escaping from half-dose CZP to full-dose CZP will receive a placebo administration and a CZP 200mg administration (a total of 2 injections) at these 3 visits ([Figure 7.1](#)).

Subjects randomized to the CZP full-dose (200mg Q2W) treatment during the Double-Blind Period who qualify for escape will remain on their current treatment allocation. As with subjects escaping from half-dose CZP to full-dose CZP, these subjects will receive a placebo and CZP 200mg injection (a total of 2 injections) at the 3 visits after the flare in order to maintain the blind to the randomized treatment.

After the loading dose (200mg Q2W or 400mg Q2W), all escaped subjects will continue full-dose CZP treatment in an open-label fashion.

The definition of flare is provided in [Section 3](#).

At the Investigator's discretion, the subject may be withdrawn from the study at any time (eg, to receive alternative treatment for the disease).

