14.1 Definition of analysis sets

The Enrolled Set (ES) will consist of all subjects who have given informed consent.

The Open-Label Set (OLS) will consist of all subjects who receive at least 1 dose of study medication in the Open-Label Period of the study (Part A).

The Randomized Set (RS) will consist of all subjects randomized into Part B of the study.

The Flared Set (FS) will consist of all subjects from the RS who experience a flare in Part B.

The Part B Full-Dose Set (FDS) will include all subjects from the RS who ever received a dose of CZP Q2W during Part B (including escape treatment).

The Safety Set (SS) will consist of all subjects in the ES who have received at least 1 dose of study medication.

The Safety Set Part B (SSB) will consist of all subjects in the RS who have received at least 1 dose of study medication in the Double-Blind Period of the study (Part B).

The Full Analysis Set (FAS) will consist of all subjects in the RS who have received at least 1 dose of study medication in Part B, and have valid ASDAS measurements at Week 48 and at least 1 timepoint following Week 48.

The Per Protocol Set (PPS) will be used to evaluate the sensitivity of the results of the primary efficacy analysis, which is based only on subjects who enter Part B. As such, the PPS will consist of subjects in the FAS without any major protocol deviations that may influence the validity of the data for the primary efficacy variable. Important protocol deviations will be defined and evaluated prior to unblinding.

The Pharmacokinetic Set A (PKSA) will consist of all subjects from the OLS who provide at least 1 PK sample during Part A.

The Pharmacokinetic Set B (PKSB) will consist of all subjects from the SSB who provide at least 1 PK sample during Part B.

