Change from Baseline in SIJ SPARCC and spine ASpIMRI-a in the Berlin modification scores at Week 96 will be compared between treatment groups using analysis of covariance (ANCOVA) for observed values only (ie, no imputation). The model will include Baseline score, treatment group, region, and mNY criteria (yes/no). Tables will present the adjusted means for placebo and the CZP doses (200mg Q2W and 200mg Q4W), the respective difference to placebo, the corresponding p-value, and 95% CI.

The binary secondary efficacy variables (ASDAS-MI, ASDAS-CII, ASAS20, ASAS40, ASAS5/6, ASAS PR, and BASDAI50 response) at Week 96 will be analyzed using a logistic regression. The odds ratio of the responder rates at Week 96 will be estimated and tested

between treatment groups using a logistic regression model with factors of treatment group, region, and mNY criteria (yes/no). Tables will present the responder rates for placebo, CZP 200mg Q2W, and CZP 200mg Q4W, the respective effect estimates (adjusted odds ratio with reference to placebo), p-values, and 95% CIs. Subjects with a missing responder status at Week 96 will be treated as a nonresponder for analysis purposes (ie, NRI).

Ankylosing Spondylitis Disease Activity Scores (ASDAS-ID, ASDAS-MD, ASDAS-HD, ASDAS-vHD) will be summarized by treatment group using summary statistics (counts and percentages) based on observed case data.

In addition to the analyses mentioned above, descriptive statistics (number of available observations [n], mean, median, SD, minimum, and maximum) will be provided by treatment group for the secondary efficacy variables. The descriptive analyses will be covered in the tables summarizing the variables over time. This will include a summary of the actual values, change from Baseline (Week 0), and change from randomization Baseline (Week 48). The statistical comparisons described for secondary efficacy variables are not part of the multiplicity-controlled testing procedure described in [Section 14.2](#). The p-values reported for these analyses will not be adjusted for multiplicity and will be considered nominal. All analyses and summaries of secondary efficacy variables in Part B will be based on the RS.

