14.3.3.3 Part B analysis for subjects who experience a flare

The other efficacy variables for subjects who experience a flare in Part B as outlined in [Section 4.1.3.3](#) will be summarized by visit and randomized treatment group using descriptive

statistics for the timepoint itself and for the change from Baseline. A subset of variables will summarize the change from randomization Baseline (Week 48) and the change from the visit at which the flare occurred. This will be done for the FS using observed case data.

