14.6 Handling of dropouts or missing data

For the primary efficacy variable (percentage of subjects in Part B who do not experience a flare), an approach based on the principles of NRI will be used to impute missing values. Specifically, if a subject withdraws from Part B at any point, they will be considered as having not responded to treatment. Therefore, they will be assumed to have experienced a flare during Part B for analysis purposes. If a subject has an intermittent missing ASDAS score (ie, a missing value at 1 visit but nonmissing values at the previous and subsequent visit), then the missing value will be ignored and flare will be based on the 2 available values. If the ASDAS score is missing at 2 or more consecutive visits, then the subject will be treated as having experienced a flare (even if ASDAS scores are available after the missed visits).

For the time to flare endpoint, the rules as described above for the primary endpoint will be applied to account for missing data when determining whether or not a subject experienced a flare. Subjects who discontinue the study without meeting the criteria for flare will be censored

at the time of their last study visit. Subjects who complete the study without meeting the criteria for flare will be censored at their Week 96 visit.

Selected continuous secondary efficacy variables will be analyzed using MMRM methods (see [Section 14.3.2.2](#) for details). Missing data for binary response secondary efficacy variables will be handled using NRI. Secondary variables related to MRI will be analyzed based on the observed case data.

In general, other efficacy variables will be summarized as both observed case and with imputation (NRI for binary response variables and LOCF for continuous variables), unless otherwise specified. Nonresponse imputation is implemented by treating missing data for binary response variables as a nonresponse. The LOCF summaries will impute missing continuous data using the last post-Baseline nonmissing result. In the event that a subject has no post-Baseline data for a given continuous variable, no imputation will be performed.

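### Response to retreatment after a flare is to be summarized on observed cases only, which contradicts the protocol's own nonresponse rule for binary secondary variables and is likely to overstate response at Escape Week 12

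*Protocol*

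**What the plan says.** Protocol Section 3.2 makes retreatment a secondary objective: "Evaluate the efficacy of re-initiation of treatment with the CZP full-dose in subjects who experience a flare following a withdrawal or dose reduction of CZP". Section 4.1.2.3 lists its secondary variables and sets their timepoint at Escape Week 12. For the binary ones, Section 14.3.2.3 says that "counts and percentages at Escape Week 12 visit will be displayed", next to the same figures at the visit where the flare criteria were met. It then fixes the missing-data rule: "All Part B summaries after subjects experience a flare will be based on observed case data and will use the FS". Section 14.1 defines the set: "The Flared Set (FS) will consist of all subjects from the RS who experience a flare in Part B".

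Three other places handle the same kind of variable differently:

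- Section 14.6: "Missing data for binary response secondary efficacy variables will be handled using NRI". The paragraph sets MRI variables apart as observed case but makes no exception for post-flare variables.
- Section 14.3.2.2, for the same binary variables at Week 96: "Subjects with a missing responder status at Week 96 will be treated as a nonresponder for analysis purposes (ie, NRI".
- Section 14.3.2.1, for ASDAS-MI and ASDAS-CII in Part A: both an NRI and an observed-case summary.

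On leaving the study after a flare, Section 6.3.2 says that, at the Investigator's discretion, "the subject may be withdrawn from the study at any time (eg, to receive alternative treatment for the disease".

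**The concern.** An observed-case percentage divides responders by the subjects who have an Escape Week 12 value. A flared subject who leaves earlier because retreatment is not working is a treatment failure, but drops out of that denominator.

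The protocol makes such exits plausible. Section 6.3.2 gives alternative treatment as its example of a reason to withdraw after escape. Section 7.8.2 requires withdrawal before any prohibited medication is started, and its list includes other biologics. In justifying the mixed model, Section 14.3.2.2 assumes that most Part B discontinuations result from reduced efficacy.

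At stake is the figure that answers a stated secondary objective: how many subjects respond again once full-dose treatment resumes. The comparison with the flare visit is affected too. The flare-visit column can contain subjects who are absent from the Escape Week 12 column, so part of an apparent recovery may only reflect who stayed.

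**Working it through.** **1. Do the rules conflict?** Section 14.3.2.3 covers all post-flare summaries and allows only observed case. Section 14.6 covers binary secondary variables and requires NRI. ASDAS-CII, ASDAS-MI and the ASAS responses at Escape Week 12 fall under both, so the conflict is real for these variables.

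It does not extend to the four-category ASDAS state. Section 14.6 does not cover that variable, and Section 14.3.2.2 uses observed case for it at Week 96 as well. Nor does it extend to the other post-flare variables. Section 14.3.3.3 says of them, "This will be done for the FS using observed case data", but for other efficacy variables Section 14.6 yields where something else is specified.

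**2. Planned number of flares.** Section 14.8 assumes 70 subjects per arm and flare-free proportions of 80% (full dose), 75% (half dose) and 45% (placebo). These inputs reproduce its stated power of 98% and 94% closely: Fisher's exact test gives 98.9% and 94.0%. Expected flares are:

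- placebo: 70 × 0.55 = 38.5
- half dose: 70 × 0.25 = 17.5
- full dose: 70 × 0.20 = 14

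The objective concerns flares after withdrawal or dose reduction, so 38.5 + 17.5 = 56 flares are relevant; with full dose the total is 70. These are upper figures if the assumed proportions already count withdrawals as flares, as the primary analysis does (Section 14.3.1).

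**3. Observed case against NRI.** Let OC be the observed-case response rate, d the share of flared subjects without an Escape Week 12 value, and f the response rate that those subjects would have shown.

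- Rate in all flared subjects = OC × (1 − d) + f × d
- Overstatement by observed case = d × (OC − f)
- NRI sets f = 0, so NRI = OC × (1 − d) and the gap is OC × d

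The protocol gives neither d nor a post-flare response rate. With OC from 60% to 90% and d from 5% to 20%, all assumed:

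| OC | d | NRI | Gap (points) |
|---|---|---|---|
| 60% | 5% | 57% | 3 |
| 60% | 20% | 48% | 12 |
| 80% | 10% | 72% | 8 |
| 80% | 20% | 64% | 16 |
| 90% | 5% | 85.5% | 4.5 |
| 90% | 20% | 72% | 18 |

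In counts:

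- Of 56 placebo and half-dose flares, 6 leave and 40 of the remaining 50 respond: 40/50 = 80.0% against 40/56 = 71.4%.
- Of 38 placebo flares, 4 leave and 27 of the remaining 34 respond: 27/34 = 79.4% against 27/38 = 71.1%.

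**4. What the gap means.** It is the overstatement only if every missing subject is a nonresponder. At OC = 80% and d = 10%, the rate in all flared subjects is 72% if f = 0, 72% + 4% = 76% if f = 40%, and 80% if f = 80%. Observed case is right when leavers would respond as often as stayers, and too high when they would respond less often.

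**The case against.** **The conflict cuts both ways.** If Section 14.6 governs, NRI already applies to the binary variables and nothing is overstated. That is logically correct. But Section 14.3.2.3 is the more specific text and says that it covers all post-flare summaries, so an analyst would more naturally follow it. The passages need reconciling on either reading.

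**Missing does not mean failed.** A reader might infer that the subjects without an Escape Week 12 value are the retreatment failures, so that the bias is always upward with nothing to offset it. The documents do not support this. Section 6.3.2 permits withdrawal but does not predict it. Failures who stay are counted as observed nonresponders. Section 6.3.1 lists exits unrelated to efficacy, such as pregnancy, TB findings or withdrawn consent, and for these NRI can err downward.

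**A leaver may still be a responder on paper.** ASDAS-CII and ASDAS-MI are measured against Week 0 (Section 9.1.7), and a flare can be ASDAS of 2.1 or more at two consecutive visits (Section 3). A subject at 3.6 at Baseline and 2.3 at flare has improved by 1.3, which still meets the 1.1 threshold for ASDAS-CII. NRI rates are therefore imputed values, not true response rates.

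**Withdrawal Visit data exist.** Sections 6.3.1 and 8.7 require these assessments. The SAP may map them to Escape Week 12, which would reduce the loss. Section 14.3.2.3 provides no such mapping, but its absence from the protocol is not a fault.

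**The tables are descriptive and show counts.** This stands and limits the consequence. A reader given the set size could divide responders by all flared subjects. That works only if the set excludes flares assigned by imputation, which the definition in Section 14.1 leaves open.

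**Conclusion.** The contradiction between Sections 14.3.2.3 and 14.6 is certain for the binary Escape Week 12 variables. The observed-case rule also departs from the handling of the same variables at Week 96 and of ASDAS-MI and ASDAS-CII in Part A.

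If Section 14.3.2.3 is followed, the percentages are likely to overstate response to retreatment, because the protocol's own rules and assumption point to exits that are mostly related to efficacy. The size is unknown: the 3 to 18 points rest on assumed response and loss rates and on counting every missing subject as a nonresponder. With no efficacy-related exits before Escape Week 12, this source of overstatement is absent.

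A reader might go further and treat the NRI figure as the true rate, apply the point to all 70 planned flares, or see a threat to the primary result. None of these follows. NRI is a conservative convention. The objective concerns at most about 56 planned flares, since full-dose subjects who flare continue full dose. The post-flare summaries are untested and separate from the primary comparison.

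**What to change.** In Section 14.3.2.3:

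- Make NRI the main summary for ASDAS-CII, ASDAS-MI, ASAS20, ASAS40, ASAS5/6 and ASAS PR at Escape Week 12, by randomized arm.
- Use as denominator all subjects who met the ASDAS flare criteria, excluding flares that exist only through the imputation rule of Section 14.3.1. Do not also require an escape dose, because that would drop subjects who flare and leave before escape.
- Show the flare-visit column on the same denominator.
- Keep observed case as supportive, and report the number missing with reasons.
- For the four-category ASDAS table, add a missing row on the same denominator. Applying NRI to inactive disease alone would put the categories on different bases.
- Align the wording with Section 14.6 so that one rule governs.

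The cost is a few sentences and some extra table columns, with no new data collection. The downside is that NRI is conservative for exits unrelated to efficacy, and the reported percentages will be somewhat less favourable.

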14.3.3 Other efficacy analyses

14.3.3.1 Part A

The other efficacy variables for Part A as outlined in [Section 4.1.3.1](#) will be summarized by visit and treatment group using descriptive statistics for the timepoint itself and for the change from Baseline. This will be done for the OLS using observed case data and with imputation using LOCF. Further details are described in the SAP.

Tables for the binary variables will display the responder rates for the various timepoints over time. This will be done for the OLS using observed case data and with imputation using NRI.

14.3.3.2 Part B

Treatment group comparisons for both CZP groups vs placebo will be performed based on the change from Baseline in other selected efficacy variables. These analyses will be performed using an ANCOVA model with variables of Baseline score, treatment group, region, and mNY criteria (yes/no) in the model. The treatment differences and corresponding 95% CIs will be calculated based on the adjusted means. Missing values will be imputed using LOCF. This analysis approach will be used for the following variables:

- Total spinal pain
- Nocturnal spinal pain
- PtGADA
- Morning stiffness (BASDAI 5 and 6)
- SF-36 PCS, MCS, and physical function domain
- Fatigue NRS
- ASQoL

Such analyses will also be done for the following continuous variables: ASDAS, BASDAI, BASFI, and BASMI will be analyzed using a MMRM similar to the one specified in [Section 14.3.2.2](#) at timepoints not covered in the secondary efficacy analyses. Additionally, ASDAS-MI, ASDAS-CH, ASAS, and BASDAI50 response variables will be analyzed using a logistic regression model similar to the one specified for binary response variables in [Section 14.3.2.2](#) at timepoints not covered in the secondary efficacy analyses.

These comparisons are not part of the multiplicity-controlled testing procedure described in [Section 14.2](#). The p-values reported for these analyses will not be adjusted for multiplicity and will be considered nominal. Exploratory statistical comparisons will also be performed for WPS scores using the nonparametric bootstrap-t method. This will be explained in greater detail in the SAP.

All other efficacy variables will be summarized descriptively by visit and treatment group using observed case and imputed data based on the RS.

14.3.3.3 Part B analysis for subjects who experience a flare

The other efficacy variables for subjects who experience a flare in Part B as outlined in [Section 4.1.3.3](#) will be summarized by visit and randomized treatment group using descriptive

statistics for the timepoint itself and for the change from Baseline. A subset of variables will summarize the change from randomization Baseline (Week 48) and the change from the visit at which the flare occurred. This will be done for the FS using observed case data.

14.4 Planned safety and other analyses

14.4.1 Safety analyses

The frequency of all AEs by study period (Part A and Part B) will be presented separately by System Organ Class, high-level term, and preferred term and for Part B by each treatment group. The data will be displayed as number of subjects experiencing the AEs, percentage of subjects, and number of AEs. Data will also be corrected for exposure by 100 patient years.

Laboratory evaluations and vital signs will be analyzed over time in the SS and SSB for observed cases and at the end of treatment.

14.4.2 Pharmacokinetic and immunogenicity analysis

Certolizumab pegol plasma concentrations will be tabulated and summarized by treatment group for each visit at which samples were taken using the geometric mean, 95% CI, geometric coefficient of variation, arithmetic mean, arithmetic SD, median, minimum, and maximum.

Immunogenicity will be assessed through listing of individual results by subject and summary tables. Immunogenicity data will be correlated with PK and efficacy readout. In addition, immunogenicity will be correlated with possible safety findings.

14.5 Handling of protocol deviations

Important protocol deviations are deviations from the protocol that could potentially have a meaningful impact on study conduct or on the primary efficacy outcomes for an individual subject. The criteria for identifying important protocol deviations will be defined within the appropriate protocol-specific document. Important protocol deviations will be reviewed as part of the ongoing data cleaning process and all important deviations will be identified and agreed upon prior to unblinding to confirm exclusion from analysis sets.

